 - achieving DAPSA remission at 6 and 12-months (including sustained)
 - achieving ACR remission at 6 and 12 months (including sustained)
 - with X-ray structural progression (mSVH score) at 12 and 24 months
 - with US structural progression (US-damage score) at 12 and 24 months
 - with functional worsening (Δ HAQ>0.23) at 12 and 24 months
 - with impairment of Health Related Quality of Life (HRQoL) at 12 and 24 months;
- to evaluate the relationship between time-integrated US-detected inflammation and US-detected damage at 12 and 24 months;
- to evaluate the comparative effectiveness of different treatment strategies on MDA, DAPSA remission, Δ HAQ>0.23, X-ray progression (mSvHS), US-inflammation score, US-damage score;
- to evaluate residual US activity in patients in MDA remission;
- to explore whether clinically-detected disease activity due to joint tenderness without swelling is related to joint or extra-articular US-detected inflammation evaluated by US;
- to explore clinical features and US-lesions related to X-ray detected bony apposition.

STUDY DESIGN

The study follows a multi-centre observational prospective cohort study design.

The study is registered at Open Science Framework.⁽¹⁶⁾

PARTICIPANTS

CENTRE SELECTION

All the members of the Italian Society of Rheumatology will be invited to participate to the UPSTREAM Study. In order to increase the validity and reliability of the results, the participants will be selected based on three prerequisites:

- local availability of a high level US machine including high level US probes (>14MHz);
- reliability exercise on static images with a kappa statistics value >0.7 compared with a 'gold standard' scorer;
- quality assessment of US images of PsA lesions.

PATIENT SELECTION

INCLUSION CRITERIA

- Adult > 18 years of age with PsA (according to the CASPAR classification Criteria)
- Clinically active arthritis, with at least one joint clinically involved (both swelling and tenderness) in patient not achieving the MDA;
- Subject newly prescribed NSAIDs (monotherapy), steroid intra-articular injections (monotherapy), cDMARD, bDMARDs as indicated by the treating rheumatologist according to usual clinical practice before US acquisition;
- Stable treatment before treatment modification (6 weeks);
- Signed informed consent form;

STUDY PROCEDURES

RELIABILITY EXERCISE

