US IMAGING						
US-score PsA-SIR		X		X	X	X
CR IMAGING						
X ray (hands-feet)		X			X	X
ADVERSE EVENTS			X	X	X	X

STATISTICAL ANALYSIS PLAN

VARIABLES: OUTCOME MEASURES

PRIMARY:

- MDA at 6 months

SECONDARY

- MDA at 12 months, sustained MDA at 6 AND 12 months
- DAPSA <3.3 at 6 months, 12 months, 6 AND 12 months
- Δ mSvH 0-12 and 0-24 months
- Δ HAQ 0-12 and 0-24 months
- Δ PSAID 0-12 and 0-24 months
- US-score PsA-SIR damage subscore at 0-6-12 months

US PREDICTORS

- US-score PsA-SIR
- US-score PsA-SIR inflammation subscore
- US-score PsA-SIR damage subscore

CLINICAL PREDICTORS

Based on the relevant literature clinical variables to be considered in the model include:

- Demographic and environmental factors:
 - Age
 - Gender
 - Smoking
 - BMI
- Clinical factors:
 - subset of PsA
 - time from symptoms onset to diagnosis
 - disease duration
 - disease activity (DAPSA and BASDAI)
 - HAQ score
 - tender joints / pain
 - comorbidities (FM, MetS)
- Serological factors:
 - Acute phase reactants
- Therapy factors:
 - Treatment (NSAIDs, steroids, DMARDs)

DESCRIPTIVE ANALYSES

Descriptive data will be provided for all outcomes according to data type; number of patients (N), mean, standard deviation (for interval data), median 25% and 75% quartiles (for ordinal data). Frequency (absolute and relative) distributions will be provided for categorical data. Two-sided p-values will be presented throughout.

PRIMARY ENDPOINT ANALYSIS

Prediction of 6 months MDA will use multivariate adjusted logistic models. A baseline model will include all the clinical variables. US predictors will be added as covariates to the clinical variables, assuming an additive model. The derived β coefficients were used to calculate prognostic indices, thereby creating weighted prediction models.

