Model performance will be evaluated by C-indices (area under the ROC curve, AUC), net reclassification indices (NRI), integrated discrimination improvement (IDI), and plotted ROC curves. NRI can be used to compare the clinical impact of different models (it is a comparison of the proportion of subjects with disease who have appropriately increased risk scores with the new model, and the proportion of subjects without disease who have appropriately decreased risk scores with the new model). IDI represents desired improvements in average sensitivity corrected for undesirable increases in 1-specificity, it therefore compared whether the new models improved sensitivity without affecting specificity.⁽³⁰⁾

Data management and analysis will be performed using RedCap, R, Stata.

SECONDARY ENDPOINT ANALYSES

- to evaluate the additional value of US over clinical examination in detecting patients:
 - achieving MDA at 12 months
 - achieving sustained DAPSA remission at 6 and 12-months
 - achieving DAPSA remission at 6 and 12 months
 - achieving ACR Remission remission at 6 and 12 months
 - with X-ray structural progression (mSVH score) at 12 and 24 months
 - with US structural progression (US-damage score) at 12 and 24 months
 - with functional worsening (Δ HAQ>0.23) at 12 and 24 months
 - with impairment of HRQoL at 12 and 24 months

The same approach followed for the primary endpoint will be followed to evaluate

EXPLORATORY ANALYSES

- to evaluate the relationship between time-integrated US-detected inflammation and US-detected erosions at 12 and 24 months
- to evaluate the comparative effectiveness of different treatment strategies on MDA, DAPSA remission, Δ HAQ>0.23, X-ray progression (mSvHS), US-inflammation score, US-damage score.
- to evaluate the comparative effectiveness of different treatment strategies on MDA, DAPSA remission, Δ HAQ>0.23, , X-ray progression (mSvHS), US-inflammation score, US-damage score.

SAMPLE SIZE

The sample size calculation was done with the objective of minimizing the number of false positives (i.e the number of false non-responsive to treatment) in order to minimize the risk of over-treating patients who actually have a good response to therapy. Therefore, sample size was calculated to minimize this risk by 40% (null hypothesis H0) to 20% (alternative hypothesis H1), maintaining stable at 70% (both for the H0 for both the H1), the percentage of true positives (true unresponsive to therapy).

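### For US-damage progression, baseline US damage is part of the outcome yet enters only the model with ultrasound, so the gain credited to ultrasound cannot be interpreted

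*Combined protocol and SAP*

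**What the plan says.** The SAP's primary endpoint analysis compares two logistic models. In the first, "A baseline model will include all the clinical variables". In the second, "US predictors will be added as covariates to the clinical variables, assuming an additive model". Performance is judged by AUC, NRI and IDI.

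The clinical list is introduced as "Based on the relevant literature clinical variables to be considered in the model include". It covers demographics, PsA subset, diagnostic delay, disease duration, "disease activity (DAPSA and BASDAI"), HAQ, tender joints or pain, comorbidities, acute phase reactants and treatment. It does not contain baseline mSvH, baseline PsAID-12 or baseline US damage. The baseline visit and the visit schedule provide for the hand and foot films, PsAID-12 and the US score.

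The US predictors are the overall score, the inflammation subscore and the "US-score PsA-SIR damage subscore". The damage subscore is also listed as a secondary outcome. The secondary objectives and the secondary endpoint analyses both include patients "with US structural progression (US-damage score) at 12 and 24 months". The radiographic outcome is "Δ mSvH 0-12 and 0-24 months".

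The only statement of method for these endpoints is "The same approach followed for the primary endpoint will be followed to evaluate". It stops there.

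**The concern.** An added-value comparison is meaningful when the two models differ only in the information being tested. For US-damage progression they also differ in whether they contain the starting value of the outcome. The clinical model has no such value; the US model has it in the damage subscore and again inside the overall score.

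A patient whose baseline scan was scored too high by chance will tend to show less apparent progression, and one scored too low will tend to show more. A logistic model will use that pattern, and AUC, NRI and IDI will count it as a contribution from ultrasound. The study could then report that US predicts structural damage when part of the signal is scoring error shared by predictor and outcome. It could also report no value because the error cancelled a real association.

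X-ray progression raises a weaker, conditional version of the question. US erosions and bony proliferation may stand in for damage already visible on the baseline film, which the clinical model does not contain.

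**Working it through.** The plan gives no figure for the secondary models, so there is none to reproduce. Every reliability, correlation and odds ratio below is an assumption.

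**1. Where the baseline outcome sits.**

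| Endpoint | Baseline value in clinical model? | Baseline value in US model? |
|---|---|---|
| HAQ worsening | yes | yes |
| PsAID-12 impairment | no | no |
| X-ray progression (mSvH) | no | no, but US damage may act as a proxy |
| US-damage progression | no | yes, as the damage subscore and within the overall score (470 + 162 = 632) |

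**2. Coupling for US damage, no true association.** Let true baseline damage have variance 1, reliability R, error variance k = (1 − R)/R at each scan, and true change of variance v independent of baseline. The correlation between observed baseline and observed change is

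r = −k / √[(1 + k)(2k + v)].

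The top 20% of change are called progressors. The AUC is for lower baseline damage pointing to progression; the logistic model picks this sign by itself. Without error the AUC would be 0.50.

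| R | v | k | r | AUC of baseline damage alone |
|---|---|---|---|---|
| 0.70 | 0.1 | 0.429 | −0.429/√(1.429 × 0.957) = −0.37 | 0.68 |
| 0.90 | 0.3 | 0.111 | −0.111/√(1.111 × 0.522) = −0.15 | 0.57 |
| 0.95 | 0.1 | 0.053 | −0.053/√(1.053 × 0.205) = −0.11 | 0.56 |
| 0.95 | 0.3 | 0.053 | −0.053/√(1.053 × 0.405) = −0.08 | 0.54 |

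A separate simulation put baseline damage into a model that already held a clinical score (200,000 subjects, reliability 0.80 to 0.95, SD of true change 0.2 or 0.4 of the true baseline SD). AUC rose by 0.016 to 0.132 from coupling alone, for example from 0.537 to 0.614 at reliability 0.90 with SD 0.2.

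**3. The direction is not fixed.** If true change correlates ρ with true baseline damage, the covariance of observed baseline and observed change is ρ√v − k. With ρ = 0.2, v = 0.3 and R = 0.9, this is 0.110 − 0.111 ≈ 0. The apparent AUC is 0.50, although true damage discriminates true progression with AUC 0.60. The coupling then masks a real relation.

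**4. After the correction.** With baseline damage in both models, an inflammation subscore with no true effect (assumed correlation 0.4 with true damage) still gains about 0.002 to 0.012 in AUC across the runs. Inflammation carries some information on true damage, so it helps to separate true baseline from scoring error. The residual is larger if true damage drives progression.

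**5. X-ray.** US was made informative only through baseline mSvH (US–mSvH correlation 0.4 to 0.6, clinical–mSvH correlation 0.3, about 20% progressing). With odds ratios of 1.5 to 2.5 per SD of mSvH, adding US gained 0.006 to 0.040 when mSvH was left out. Stronger assumed effects (log-odds up to 1.0 per SD) took the gain to about 0.08. With mSvH in both models the gain was 0.000 throughout.

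**6. PsAID-12.** With a clinical–PsAID correlation of 0.6 to 0.8 and a US–PsAID correlation of 0.2, the spurious gain was 0.000 to 0.002.

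**The case against.** - **The plan is incomplete rather than wrong.** The clinical variables are offered for consideration and the key sentence is unfinished, so baseline outcomes are not explicitly excluded. That is fair. But the reference model is then said to take in all the listed variables, and nothing adds a baseline outcome. Leaving the choice until the data are seen matters here, because it affects the apparent US gain.
- **Change from baseline is inferred.** The SAP writes a difference for mSvH, HAQ and PsAID, but lists the US damage subscore by time point, without a formula or cut-off. This stands as a condition. The word progression makes a change score the natural reading, but the coupling argument depends on it.
- **The aim is value over clinical examination.** A film read centrally, after the event, is not clinical examination, so leaving mSvH out answers the question as posed. This stands for X-ray, and the mSvH-adjusted comparison belongs beside the stated one, not in its place. It does not help for US damage, where the problem is shared error between predictor and outcome.
- **A reader might infer that US is credited by construction for every progression and quality-of-life endpoint.** The documents do not support that. HAQ already has its baseline in the model. For PsAID-12, the listed DAPSA, BASDAI, HAQ and pain cover much of the missing value. For X-ray the effect depends on assumed correlations. Even for US damage, the coupling can lower the apparent value as well as raise it.

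**Conclusion.** The point holds firmly for US-damage progression, on the reading that progression is follow-up minus baseline. Followed as written, the plan gives a US gain that cannot be interpreted: an AUC of 0.54 to 0.68 can arise from scoring error alone at reliability 0.7 to 0.95, and a modest positive true association can be cancelled. The sizes rest on assumed reliability and change variance; the structural fault does not.

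For X-ray progression it is a conditional caution, with a possible spurious gain of about 0.006 to 0.08 under assumed inputs. For PsAID-12, adding the baseline is a matter of consistency with HAQ, with almost no credit passing to US.

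These are secondary endpoints and the primary MDA analysis is untouched. This is a cheap improvement, not a threat to the study's main conclusion.

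**What to change.** 1. Complete the unfinished sentence in the secondary endpoint analyses and name the covariates for each endpoint. State how US and X-ray progression and quality-of-life impairment are calculated and what cut-offs apply. Reconcile the US-damage time points: 0, 6 and 12 months in the SAP outcome list, 12 and 24 months in the objectives and analyses.
2. For US-damage progression, put the baseline damage subscore in both models and test only the inflammation subscore as the added US predictor, not the damage or overall score. The overall score is the sum of the two subscores, so in a linear predictor that already holds damage it brings nothing beyond inflammation. State that a small gain (about 0.002 to 0.012 in AUC in the null simulations, more if true damage drives progression) can remain because the baseline is measured with error.
3. For X-ray progression, keep the comparison over clinical examination and report beside it the comparison with baseline mSvH in both models.
4. For quality-of-life impairment, add baseline PsAID-12 to both models, as is already the case for HAQ.

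The cost is SAP wording and one degree of freedom per secondary model, using data already scheduled for collection. The reported US gain may be smaller.

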The simulations were carried out using the procedure `rocsz` Stata (by M. Pepe)³⁰, which allows to determine the power to detect an improvement in the ROC curve. The procedure requires the specification of the percentage of false positive and true positive both for the null hypothesis is for the alternative hypothesis and the percentage of positive / diseased.

Using the command `rocsz 0.7 0.2, na (150) ndb (100) tnull (0.7) fnull (0.4)` of Stata, 250 patients are sufficient to evaluate the performance of a model (and its ROC curve) with 90% power and 5% alpha. Specifically, we have assumed a 70% and a 20% of subjects true positives and false positives, respectively, according to the alternative hypothesis, a 70% and a 40% of subjects true positives and false positives, respectively, according to the null hypothesis, and a percentage of diseased of 60% (150 of 250 subjects).

Under the assumption of maximum attrition of 20%, the sample size will be increased to 300 patients. The same sample size is sufficient to precisely estimate a logistic model of achievement of a MDA (probability of 0.4 at 6 months) with 10 predictors (rule of thumbs).⁽³¹⁾

Based on the pre-study activities, 35-40 centres will be involved, 15 tertiary and 20-25 secondary rheumatology centres. Assuming 4 eligible patients/months for tertiary and 1/month in secondary centres, a 40% of enrolment rate, about 30 patients/months are expected.

ETHICS

This study will be conducted in accordance with all applicable laws and regulations including, but not limited to, the International Conference on Harmonisation (ICH) Guideline for Good Clinical Practice (GCP), EU guidelines and the ethical principles that have their origins in the Declaration of Helsinki. The institutional review board (IRB)/independent ethics committee (IEC) must review and approve the protocol and informed consent form before any subjects are enrolled. Before any protocol-required procedures are performed, the subject must sign and date the IRB/IEC-approved informed consent form.

Clinical data (including AEs and concomitant medications) will be entered into a validated data capture system provided by the Italian Society for Rheumatology. The data system will include password protection and internal quality checks, such as automatic range checks, to identify data that appear inconsistent, incomplete, or inaccurate.

PUBLICATION RULES

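### The stated 90% power belongs to a false-positive rate at 70% true positives, which the primary analysis does not estimate or test

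*Combined protocol and SAP*

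**What the plan says.** The SAMPLE SIZE section starts from the aim of "minimizing the number of false positives (i.e the number of false non-responsive to treatment", so that patients who are responding well are not over-treated. It then states that the "sample size was calculated to minimize this risk by 40% (null hypothesis H0) to 20% (alternative hypothesis H1", while "maintaining stable at 70% (both for the H0 for both the H1), the percentage of true positives (true unresponsive to therapy". The Stata call is "rocsz 0.7 0.2, na (150) ndb (100) tnull (0.7) fnull (0.4", with 150 non-responders counted as diseased and 100 responders as not diseased. The conclusion is that "250 patients are sufficient to evaluate the performance of a model (and its ROC curve) with 90% power and 5% alpha".

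The PRIMARY ENDPOINT ANALYSIS section says "Prediction of 6 months MDA will use multivariate adjusted logistic models": a clinical model first, then the same model with the ultrasound predictors added. On comparison it says "Model performance will be evaluated by C-indices (area under the ROC curve, AUC), net reclassification indices (NRI), integrated discrimination improvement (IDI" and adds plotted ROC curves. It gives no cut-off, no fixed true-positive rate, no comparison of false-positive rates, and no test or interval for such a comparison.

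**The concern.** The sizing hypothesis concerns one point on the ROC curve. AUC and IDI summarise over all thresholds. NRI, as the plan describes it, counts risk scores that move in the right direction. None of these is the rate that H0 and H1 refer to.

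A reader who sees 90% power will assume that it covers the main comparison, and it does not. The trial could report a favourable AUC, NRI or IDI while the number of good responders wrongly labelled non-responsive had barely changed. If that rate is worked out only after the results are known, the cut-off becomes a post hoc choice.

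**Working it through.** **Inputs.** From SAMPLE SIZE: false-positive rate f = 0.40 (H0) and 0.20 (H1); true-positive rate t = 0.70 under both; 150 positives and 100 negatives; 90% power; 5% alpha; MDA probability 0.4. The sizing does not state sidedness, though DESCRIPTIVE ANALYSES says "Two-sided p-values will be presented throughout". ROC shape and test statistic are not given, so those used below are assumptions.

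**1. The plan's own 90%.**
- Simple proportion in 100 negatives against a fixed 0.40, two-sided score test: (0.20 − 1.96·√(0.40·0.60/100)) / √(0.20·0.80/100) = (0.20 − 0.096)/0.040 = 2.60, so power is 99.5%.
- Cut-off estimated from the 150 positives: Var(f) = f(1−f)/100 + (df/dt)²·0.70·0.30/150. With an equal-variance binormal ROC, df/dt = φ(Φ⁻¹(f))/φ(Φ⁻¹(0.70)), which is 1.111 at f = 0.40 and 0.805 at f = 0.20. The SEs are 0.0643 and 0.0501. Power = Φ((0.20 − 1.96·0.0643)/0.0501) = Φ(1.48) = 93%.
- Over slopes 0.7 to 1.4 and score or Wald statistics, power is 80% to 99% two-sided and 89% to above 99% one-sided.

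The stated 90% lies inside this range. It cannot be reproduced uniquely, but no error is shown.

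**2. Sizing and analysis side by side.**
- Quantity: false-positive rate at 70% true positives, against AUC, NRI, IDI and a plot.
- Comparator: fixed null values of 70% and 40%, against a fitted clinical model. The inputs that the plan lists for the command do not include a second model or any correlation between models.
- Positive label: non-response, against MDA as the modelled event.

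**3. Does AUC determine the rate?** Binormal ROC: t = Φ(a + b·Φ⁻¹(f)) and AUC = Φ(a/√(1+b²)). With b = 1, a = Φ⁻¹(0.70) − Φ⁻¹(f).
- f = 0.40: a = 0.778, AUC = 0.71.
- f = 0.20: a = 1.366, AUC = 0.83.
- Inverting, AUC 0.73 gives f of about 0.36, and AUC 0.77 gives about 0.30.
- Other slopes through (0.20, 0.70), with a = 0.524 + 0.842·b: b = 0.5 gives Φ(0.945/1.118) = 0.80; b = 2 gives Φ(2.208/2.236) = 0.84.
- Conversely, a fixed AUC of 0.80 gives f between 0.20 and 0.25 for slopes 0.5 to 2.

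**4. Precision of the missing estimate.** Equal-variance binormal simulation with 150/100 patients, clinical AUC 0.709, and assumed odds ratios per SD of ultrasound score of 1.5, 2.0 and 3.07:
- AUC with ultrasound: 0.732, 0.769, 0.833.
- False-positive rate at 70% true positives: 0.36, 0.30, 0.20.
- SD of the paired difference: 0.049, 0.061, 0.066. Multiplied by 1.96, the half-widths are 0.10, 0.12 and 0.13.

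As a check on the designed effect, a paired test in 100 responders with discordance ψ and a known cut-off has power Φ((0.20·√100 − 1.96·√ψ)/√(ψ − 0.04)). This is 87% at ψ = 0.40·0.80 + 0.60·0.20 = 0.44 (independent errors) and above 99% at ψ = 0.20. Estimating the cut-off lowers both figures.

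**5. Labels.** Non-MDA is the complement of MDA: the plan's 60% diseased is 1 − 0.4. Recoding turns the point (false positive 20%, true positive 70%) into (1 − 0.70, 1 − 0.20) = (30%, 80%), the same point renamed. Nested logistic models fitted to one simulated set of 250 under both codings gave identical results: AUC 0.670 to 0.730, IDI 0.0714, NRI 0.478.

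**The case against.** The primary objective asks what ultrasound adds to clinical examination in identifying patients who reach MDA, and it names no operating point. AUC, NRI and IDI on nested models address that directly. The false-positive side is not ignored, because the plan's descriptions of NRI and IDI both bring it in. The sizing text also speaks more broadly of better ROC performance, and gives a second justification: a logistic model with 10 predictors at MDA probability 0.4 (0.4 × 250 = 100 events, 10 per predictor). All of this stands. However, the second justification is a rule of thumb for fitting a model and carries no power, and the 90% is still tied to one operating point.

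Three stronger readings are tempting, and the documents support none of them:
- That the model predicts the wrong event. MDA and non-MDA are one binary outcome, and AUC, IDI and NRI do not change with the label. Only the meaning of false positive at a cut-off changes, so the label needs stating.
- That the sizing question cannot be answered. The rate can be read from the plotted curves. Such a reading is descriptive and has no paired interval.
- That 250 patients are too few or the 90% is wrong. Step 1 does not show that.

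**Conclusion.** The gap is real and limited. The sizing hypothesis has no matching planned estimate, interval or test, and the 90% power does not carry over to AUC, NRI, IDI or a paired model comparison. AUC cannot fill the gap: on the assumed equal-variance binormal curve, a gain from 0.71 to 0.77 delivers only half of the planned 20-point reduction.

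The AUC equivalents depend on the assumed ROC shape, and the precision figures also depend on the assumed ultrasound effects. The precision figures come from a simple model, and fitted models with more predictors will be less precise. They will also look better than they are: in a simulation with 12 assumed clinical predictors, 250 patients and a true rate of 40%, the apparent rate averaged 35%, although the bias in the paired difference was only about 1 point.

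**What to change.** Add to PRIMARY ENDPOINT ANALYSIS, alongside AUC, NRI and IDI:

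> Positive means not in MDA at month 6; the same label is used for NRI and for the sample size. For the clinical model and the clinical-plus-ultrasound model, the false-positive rate will be reported at the cut-off giving 70% true positives, together with the paired difference. A bootstrap 95% CI will be given, with both models refitted and the cut-off re-derived in each resample, and with correction for optimism.

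Add to SAMPLE SIZE:

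> The rocsz calculation compared one model with fixed null values (70% true positives, 40% false positives). The 90% power refers to that contrast and not to the paired difference or to AUC, NRI or IDI.

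Whether this rate should rank above AUC is the sponsor's choice. If the sponsor would rather not add it, restating the sizing on the measure actually used would also reconcile the two sections.

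The cost is one SAP paragraph, one sample-size statement and a few lines of code, with no new data. The downside is one more pre-specified measure with a fairly wide interval.

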In PsA but also in chronic arthritis in general, integrating imaging in clinical practice is the challenge of the near future and for clinical feasibility it is essential to identify an US composite score that could explore all the domains of the disease, especially in the polymorphic PsA.

In 2012 *Gutierrez et al.* developed a Power Doppler composite score focused on joints, tendons, entheses, skin and nails and the final target was to define the overall disease activity.⁽¹³⁾ The German US7-joints score is another viable tool for examining patients with chronic arthritis in daily practice. Developed mainly for RA, it was also effective for monitoring therapy in peripheral PsA.⁽¹⁴⁾ More recently *Ficjan et al* developed two new US composite scores (PsASon-13 and PsASon-22), derived from a total ultrasound score (68 joints/14 entheses) in order to have a high sensitivity to detect PsA features and a good feasibility in clinical practice.⁽¹⁵⁾ However no simplified scores are fully validated in terms of content, construct and criterion so far. For this reason extensive US evaluations are needed to assess PsA in clinical practice and research.

AIM

The aim of this study is to identify clinical and US predictors of achieving MDA in PsA patients with active peripheral arthritis starting a new course of therapy.

Identifying prognostic factors of achieving remission or low disease activity will allow a better selection of patients with poorer outcome and a following improvement of the therapeutic strategies. Furthermore the possibility that US could be an added prognostic value makes this study a clear example of integration between the clinic and US. This study will respond to the need of tailoring treatment that would allow clinicians to practice a more effective and personalized medicine, optimizing the outcomes of patients with PsA as well as the treatments management.

STUDY OBJECTIVES

PRIMARY OBJECTIVE

In clinically diagnosed PsA with clinically active joint disease starting a new course of therapy, to evaluate the additional value of US-score (US-score PsA-SIR) over clinical examination in detecting patients achieving MDA at 6 months.

SECONDARY OBJECTIVES

In clinically diagnosed PsA with clinically active joint disease starting a new course of therapy:

- to evaluate the additional value of US over clinical examination in detecting patients:
 - achieving MDA at 12 months (including sustained)

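### The stated 90% power is for one model against a fixed ROC point, so the primary comparison (clinical-plus-US against clinical) has no power figure

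*Combined protocol and SAP*

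**What the plan says.** The primary objective is "to evaluate the additional value of US-score (US-score PsA-SIR) over clinical examination in detecting patients achieving MDA at 6 months".

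Under Primary Endpoint Analysis, a logistic model with all the clinical variables is fitted first. Then "US predictors will be added as covariates to the clinical variables, assuming an additive model". On comparison, the section says: "Model performance will be evaluated by C-indices (area under the ROC curve, AUC), net reclassification indices (NRI), integrated discrimination improvement (IDI"), together with plotted ROC curves. It names no test, minimum gain or decision rule. Under Descriptive Analyses the SAP adds: "Two-sided p-values will be presented throughout".

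The Sample Size section uses a Stata procedure that it describes as giving power to detect an improvement in the ROC curve. It explains: "The procedure requires the specification of the percentage of false positive and true positive both for the null hypothesis" and for the alternative, plus the share of diseased subjects. The command is "rocsz 0.7 0.2, na (150) ndb (100) tnull (0.7) fnull (0.4"). The alternative is spelled out as "a 70% and a 20% of subjects true positives and false positives, respectively, according to the alternative hypothesis", and the null as 70% and 40%. Diseased means not responding, 150 of 250. The conclusion is that "250 patients are sufficient to evaluate the performance of a model (and its ROC curve) with 90% power and 5% alpha". The only other sizing statement is a rule of thumb for fitting a 10-predictor logistic model, which is not a power calculation.

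**The concern.** The objective compares two models, both estimated from the same patients. The calculation concerns one model set against two constants. Nothing in the command identifies US or a clinical model, and nothing carries the uncertainty of the comparator or its correlation with the extended model.

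The 90% is the only power claim in the document, so a reader will attach it to the primary objective. If the study finds no clear gain from US, that reader will treat the result as informative at 90% power. Whether it is informative depends on the measure tested and on the size of the US effect, and the plan ties the 90% to neither.

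**Working it through.** **Inputs from the Sample Size section.** 150 patients not in MDA and 100 in MDA; null (TPF 0.70, FPF 0.40); alternative (0.70, 0.20); alpha 5%. Its sidedness is not stated there; two-sided is used below because the SAP reports two-sided p-values.

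**Assumption not in the documents.** Scores are normal with equal variance in both groups, so one separation d = z(TPF) − z(FPF) fixes the curve, and AUC = Φ(d/√2).
- Null: d = 0.524 + 0.253 = 0.778, AUC 0.709.
- Alternative: d = 0.524 + 0.842 = 1.366, AUC 0.833.

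**Step 1. Reproduce the stated 90%.**

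(a) Test TPF at FPF 0.40 against the constant 0.70. Under the alternative, TPF = Φ(1.366 − 0.253) = 0.867. Variance = T(1−T)/150 + s²·f(1−f)/100, where s is the ROC slope.
- Null: 0.21/150 + 0.900² × 0.24/100 = 0.00334, SE 0.0578.
- Alternative: 0.115/150 + 0.556² × 0.24/100 = 0.00151, SE 0.0389.
- Power = Φ((0.167 − 1.96 × 0.0578)/0.0389) = Φ(1.38) = 91.7%.

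(b) Test FPF at TPF 0.70 against the constant 0.40, on the logit scale.
- Variance = 0.16/100 + 0.805² × 0.21/150 = 0.00251, SE 0.0501.
- Logit difference = ln(0.4/0.6) − ln(0.2/0.8) = 0.981; its SE = 0.0501/0.16 = 0.313; ratio 3.13.
- Power = Φ(3.13 − 1.96) = 88% two-sided, Φ(3.13 − 1.645) = 93% one-sided.

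The 90% is therefore consistent with a one-sample ROC-point test. The number alone does not identify the test: a test of FPF as a simple proportion in 100 patients gives over 99%, and a joint requirement on TPF and FPF gives about 2–4%. The inputs settle it, because every version has one model and a fixed null.

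**Step 2. What the fixed null leaves out.** If 70/40 stands for the clinical model, its FPF is also estimated. At 0.40 the variance is 0.24/100 + 1.111² × 0.21/150 = 0.00413, SE 0.064. The one-sample test sets this to zero and needs no correlation. In a simulation of both scores in the same patients, the paired FPF difference has mean 0.198 and SD 0.066, against 0.050 in Step 1(b). Power = Φ(0.198/0.066 − 1.96) = Φ(1.04) = 85%.

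**Step 3. Power for the two-model comparison.** Further assumptions: the US score is independent of the clinical score, coefficients are known, and the clinical model sits at 70/40. Separations then combine as d² = 0.778² + d_US², and the US odds ratio per SD is exp(d_US).
- 40% to 20%: d_US = √(1.366² − 0.778²) = 1.123, OR 3.07.
- 40% to 30%: d = 0.524 + 0.524 = 1.049, d_US = 0.704, OR 2.02, AUC 0.771.
- OR 1.5: d_US = 0.405, d = 0.877, AUC 0.732, FPF = Φ(0.524 − 0.877) = 36%.

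Simulated power, 150/100, two-sided 5%:

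| US effect | Paired AUC (DeLong) | Paired FPF at 70% TPF |
|---|---|---|
| FPF 40% to 20% | about 98% | about 84–85% |
| FPF 40% to 30% | about 72% | about 38% |
| OR 1.5 per SD | about 29% | about 11% |

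**Step 4. Dependence on the unstated correlation.** The documents give none. Without the independent-score structure:
- FPF 0.40 to 0.20 at fixed cut-offs in the 100 MDA patients, with discordance ψ: power = Φ((0.2√100 − 1.96√ψ)/√(ψ − 0.04)). This is Φ(1.11) = 87% at ψ = 0.44 (independent classifications) and Φ(2.81) = 99.7% at ψ = 0.20 (fully nested).
- AUC 0.709 to 0.833, Hanley–McNeil variances: 95% at r = 0.3 and 99% at r = 0.5.
- AUC 0.709 to 0.75: 20%, 40%, 55% and 83% at r = 0.3, 0.7, 0.8 and 0.9.

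**The case against.** The best defence is that the section speaks of an improvement in the ROC curve, so its authors probably meant 70/40 as the clinical benchmark and 70/20 as the model with US. On that reading the sample is adequate: paired AUC power is 95% or more at r of at least 0.3, above the stated 90%. The low figures in the last column of the table concern the false-positive rate at fixed sensitivity, which appears only in the sizing text and is not among the planned measures (AUC, NRI, IDI).

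Much of this stands. It limits what can be claimed, but it does not turn the 90% into a two-model figure. No section labels the two points as the two models, and even under that reading the comparator is treated as known.

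Four stronger inferences are tempting and not supported:
- *The study is underpowered.* On the plan's own effect, power is about 84% or more on every two-model measure computed here.
- *A good clinical model could pass the test and US would get the credit.* The SAP never plans to test the extended model against a fixed 40%; it compares clinical with clinical-plus-US.
- *The arithmetic is wrong.* The 90% reproduces to within about three points as a one-sample figure.
- *The assumed effect is implausible.* The documents give no source for 40% or 20%, but also nothing against which to judge them. The odds ratio of 3.07 holds only for a single independent score.

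**Conclusion.** The concern holds as a mismatch between the test that was sized and the analysis that is planned. The 90% is a one-sample ROC-point figure. It omits the sampling error of the clinical model (SE about 0.064 on the FPF scale) and the correlation between models, and the primary objective is left without a power figure.

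The size of the discrepancy depends on the measure and the effect. For the effect written in the plan, two-model power is near or above 90% on AUC and somewhat below it on FPF. For moderate effects it is well below 90% on both. These figures rest on binormal scores, an independent US score where the table is used, a clinical model at 70/40, and coefficients taken as known. The last ignores model fitting and overfitting, so the figures are probably optimistic. The structural finding depends on none of these assumptions.

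**What to change.** Keep the sample size and amend the Sample Size text in three places.

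1. Relabel the 90% as the power of a one-sample test of one model's ROC point (70/20) against a fixed point (70/40), and state whether alpha is one- or two-sided.
2. Name the added-value comparison that is powered, for example the paired AUC difference between the clinical and clinical-plus-US models. Say which US predictor enters it: the SAP lists the total and both subscores, and by their ranges the total is the sum of the two (470 + 162 = 632).
3. Give the power of that comparison as a range with its assumptions. For example: with 250 evaluable patients (150/100), an equal-variance binormal model, an independent US score and known coefficients, paired AUC power is about 98% for a fall in the false-positive rate from 40% to 20% at 70% true positives, about 72% for a fall to 30%, and about 29% for an odds ratio of 1.5 per SD. If the false-positive rate at 70% true positives is kept as a measure, the matching figures are about 84–85%, 38% and 11%.

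The cost is wording only: no extra patients, visits or procedures. The downside is that a single 90% claim becomes a range that is lower for moderate US effects.
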